### 4.2 Recruitment and consent

#### ***Determining capacity***

Subjects who are conscious and appear to possess capacity to consent will view consent information with a study team member. This consent process will include a review of specified questions with the coordinator (e.g., what is the study purpose? What are the study procedures? Does this study involve treatment?). If the subject is unable to provide appropriate answers, despite review with the study team member, or if the study team member is not certain of the subject's decision making ability, then the study team will have a follow up conversation with the clinician investigator to confirm capacity. The communication should be documented in the subject's records.

Subjects assessed to be lacking consent capacity will be involved in consent discussions and asked to provide verbal 'assent' to the degree to which they are able. For subjects who are able to be involved in such discussions, they will be provided with an oral summary of the study in terms they are likely to understand. Subjects expressing dissent to participation will not be enrolled, regardless of surrogate consent.

If a subject is determined to lack the capacity to consent, a surrogate (e.g., family member) will be approached to discuss the study and to review the consent information. Surrogate priority will be:

Subject with no Research Power of Attorney, no Guardian, and no Healthcare Power of Attorney: If the potential subject is found to lack capacity, then the potential subject's next of kin may consent on behalf of the potential subject as a legally authorized representative (LAR). Any next of kin representative of the potential subject should be actively involved in the care of the subject. LAR order of priority is:

- a. spouse
- b. adult child
- c. parent
- d. adult sibling
- e. grandparent
- f. adult grandchild
- g. close friend

### ***Recruitment of potential subjects***

A study team member will approach subjects who are likely to be eligible for study participation, based on review of the potential subject's medical record and current clinical status. No study specific procedures will be performed prior to obtaining informed consent.

### ***Informed consent process***

A member of the study team will conduct the informed consent discussion with the potential subject or surrogate in a location where a private conversation may be held. The study team member will explain the study procedures, that the purpose of the study is to evaluate a new infection monitor, and that treatment of the potential subject is not the purpose of the study. Any study team member may conduct the informed consent discussion and obtain informed consent. A physician investigator will be available to address consent related questions. Coercion will be prevented by stressing that the potential subject or surrogate does not have to agree to participate, and that the care of the potential subject will not be affected by the decision to participate.

### ***Enrollment***

A subject will be considered enrolled in the study once they have been consented for participation and the first breath sample has been collected. See study definitions in section 6.1.

## **4.3 Consent of subjects who regain capacity**

Enrolled subjects will be assessed for capacity to consent daily until they complete the study. Subjects who regain capacity during their stay in the study hospital will be approached for consent to use the data and samples collected during the study. Study records of data and samples collected from subjects who decline study participation will be destroyed, with the exception of any data used for safety analysis.

Subjects who provide informed consent after regaining capacity can withdraw from the study at a later time (See 6.12 Withdrawal of subjects).

Subjects who are contacted over the phone, will be assessed for capacity and consented over the phone if necessary. Subjects who do not regain capacity to consent prior to being discharged from the study hospital, but who later regain this capacity, may contact the study site and request that their study related data and samples be deleted or destroyed. If the data or samples have already been analyzed (including for safety purposes) or de-identified, then the data used for study purposes will not be removed.

## 5.0 Study procedures

### 5.1 Baseline

The baseline period is from time of hospital admission until the first breath sample collection. Demographic data, relevant medical and surgical history, admission reason to the ICU/critically ill status, concomitant medications, and vital sign data will be collected.

### 5.2 ICU/IMC Days

This initial period of study days begins the day a subject is consented thru either discharge from the hospital or from an IMC/step-down unit to a general care status/unit. A study day will equal one calendar day. Day 1 will start at the time of the first breath collection and end at 23:59. Day 1 will typically be less than 24 hours and fewer than 6 breath samples may be collected. Research samples will be obtained until (1) the subject has been discharged to general care status/unit or (2) the subject has been discharged from hospital or (3) 28 days of breath sample collection has occurred, whichever comes first.

- Assess for capacity to consent (if subject did not previously provide consent)
- Research breath sample every 4 hours
  - Vital signs recorded concurrently
- Research blood draw once per calendar day
- Medical record abstraction

### 5.3 Post ICU/IMC Days

This period of the study will last three days beyond a subject's discharge from the ICU/IMC. If a subject is discharged home, the subject's electronic medical record (EMR) will be reviewed for an additional three days beyond discharge\* for any results, notes, procedures, or readmission information.

- Assess for capacity to consent (if subject did not provide consent and is still in the hospital)
  - Medical record abstraction
- \*If subject has been in the study for 28 days then the post ICU/IMC days will take effect on Day 29.

### 5.4 Antibiotic Use Follow-up Days (3 days beyond last dose of antibiotics)

If the subject is on antibiotics when discharged from the ICU/IMC, they will be followed for the three Post-ICU/IMC days (as detailed in 5.3) and then daily until the last dose of antibiotics (from the initial prescriptions at time of discharge), followed by an additional three days. If the subject is discharged home, the EMR will be reviewed daily until three days beyond the final scheduled dose of antibiotics. The subject will be called on the third day beyond their last anticipated dose of antibiotics to inquire about their infection/readmission status since their original hospital discharge.

- Assess for capacity to consent
- Medical record abstraction
- Phone questionnaire

## 5.5 Breath sample collection

Breath samples will be collected upon enrollment and every four hours thereafter until the subject is (1) discharged home or (2) to general care unit/status or (3) 28 days of breath sample collection has occurred, whichever comes first. Each sample should be collected in four-hour intervals, calculated from the initial sample time, with a window of  $\pm 1$  hour. The target time for sample collection will be determined when the first sample is collected and will not be reset if a subsequent sample is collected late or early. Samples collected outside of the specified time interval will still be analyzed. NOTE: Day 1 can start immediately after the baseline data collection is complete, and may occur on the same physical day. Therefore, it is likely that Day 1 won't have all 6 breath samples because of the shortened duration after the consent process.

Some subjects may be discharged from the study hospital in less than five days. If subjects are withdrawn (e.g. are discharged or died) on or before completing Day 5, they will be replaced in the overall enrollment numbers and not used in the primary analysis, though the data and breath samples collected will still be kept. Subjects who withdraw after completing Day 5, will have their data remain as part of the primary analysis. See Table 1 in section 5.12.

Breath sample collection bags will be provided by Isomark. Any unused bags will be returned to Isomark. Training documents about breath sample collection and storage are detailed in Isomark's Lab Manual. Collected samples will be labeled with site number, subject number, subject initials, date and time of collection. Collected samples will be stored in a secure location at the study hospital until sent to Isomark.

### **Mechanically ventilated subjects**

For mechanically ventilated subjects, an appropriately trained and qualified member of the subject's clinical care team or study team member will obtain expired breath from a side port adaptor in the expiratory limb of the subject breathing circuit. The gas sample will be obtained in a small gas sample bag. This method of sample collection allows inflation of a sample bag without any interference with operation of the mechanical ventilator or breathing circuit. The breath sample bag will inflate visibly during approximately 2-4 breath cycles. The bag will appear inflated, but not over inflated, after which time the sample bag will be disconnected and sealed.

#### Sampling from expiratory limb:

When sampling from the expiratory limb of the breathing circuit, the sample bag will be attached to a standard diameter, straight adaptor with a side port fitted with a normally closed valve which only opens when a sample bag is attached. The standard side port adaptor will be placed by a respiratory therapist in the expiratory limb of the breathing circuit proximal to the subject at the start of the clinical trial for the subject and will remain in place for the duration of the clinical trial for the subject or for the duration of mechanical ventilation support, or, if a breathing circuit is replaced anytime during the clinical trial for the subject, then a new adaptor will be placed.

### **Non-mechanically ventilated subjects**

Non-mechanically ventilated subjects will be asked to inflate a breath sample bag by exhaling. Subjects should repeat exhalation until the bag appears visibly inflated, but not over inflated.

### **Subjects who are having difficulty breathing (Mask Sample Collection)**

If the subject is not ventilated but has difficulty inflating a bag using the bag's mouthpiece, a mask collection option is available. Collecting a sample using the mask is performed by attaching a sample bag to the breathing mask via a connector. The mask is placed over the subject's nose and mouth during exhalation. The sample bag should appear visibly inflated, but not over inflated. If more than one breath is required to inflate the bag, the mask must be removed during inhalation.

## 5.6 Blood sample collection

Once daily during breath sample collection days, 3 mL of blood will be obtained in a green top, lithium heparin tube from subjects via an existing IV or arterial catheter. If subjects do not have an existing catheter, research samples may

be obtained via peripheral lines or venipuncture. Timing of the blood sample is not critical, but one sample is to be collected during each calendar day of the ICU/IMC Study Days period. Blood may be obtained from an artery or a vein. Collected samples will be affixed with a provided de-identified label.

To avoid sample collection from subjects who are anemic, if a subject's known hemoglobin concentration is less than 6.0 g/dL at any time, then blood collection will stop and will not resume until the subject's hemoglobin concentration has increased to greater than or equal to 6.0 g/dL. If blood sample acquisition is stopped due to hemoglobin concentration criterion, then other study activities will continue per protocol.

## 5.7 Blood sample processing, storage and analysis

Please see Isomark's Lab Manual for complete instructions. Whole blood samples will be spun down in a centrifuge. A minimum of 1.5 mL of plasma should be transferred to aliquot tubes. Plasma samples will be labeled with a duplicated label pre-printed with the subject number and the date/time of collection written. Remaining red blood cells (RBC) will be recapped in the lithium heparin tubes and stored in that tube. The plasma aliquot tubes will be kept frozen at the site for a minimum of 24 hours before batch shipping to Isomark's reference lab for later analysis of PCT and CRP. The RBC tubes will be kept frozen at the site for a minimum of 24 hours before batch shipping to Isomark for isotope ratio analysis. Following assay of these biomarkers, all samples will be exhausted or destroyed.

Study samples will be kept between -50° and -196° C until the time of analysis. The storage freezer must maintain constant temperature (i.e. must not be frost-free or defrost automatically). Study team members will report all occurrences of freezer temperature deviating outside of this range. Temperature logs from the freezer(s) will not be collected.

Clinical care providers for the study subjects and study team members will not have access to the PCT or CRP measurements until all study data and sample collection is complete. Subjects will not be informed of their individual PCT or CRP measurements.

## 5.8 Carbon isotope measurement

### ***Measuring breath carbon isotope concentration***

Please see Isomark's Lab Manual for complete instructions. Collected breath samples will be shipped to Isomark within 48 hours of final collection from a subject via a shipping service, such as UPS or FedEx, to Isomark's breath analysis lab. If multiple subjects are enrolled, then shipments should be made once per week. Isomark personnel will analyze the isotope ratio. Some of the gas sample will be withdrawn from the gas tight bag by the Canary. The CO2/CO2 ratio in each sample will be determined from direct measurement. BDV will be calculated using Pee Dee Belemnite (PDB) as a standard reference:

$$BDV = \frac{(^{13}\text{CO}_2/^{12}\text{CO}_2 \text{ sample} - ^{13}\text{CO}_2/^{12}\text{CO}_2 \text{ PDB}) \times 1000}{^{13}\text{CO}_2/^{12}\text{CO}_2 \text{ PDB}}$$

where BDV is expressed as parts per mil (‰).

### ***Results of carbon isotope measurement***

Carbon isotope measurement in exhaled CO2 is not part of standard medical treatment in any patient population. Clinical care providers for the study subjects and study team members will not have access to the carbon isotope measurements until all study data and sample collection is complete. Subjects will not be informed of their individual carbon isotope measurements.

## 5.9 Third parties

Isomark will be using reference laboratories for the analysis of CRP and PCT as well as for the red cell carbon isotope concentration. These laboratories will analyze study samples and provide results to Isomark personnel who will distribute to sites for documentation and data entry. If a third party were to require the study samples for another study related analysis, an amendment to this protocol would be submitted, and only de-identified information would be available to the third party.

### ***Measuring C-reactive Protein and Procalcitonin***

Study samples will be stored in the freezer until batch shipped to the central laboratory, Marshfield Laboratories, for biomarker analysis. Marshfield Laboratory has been contracted to analyze the CRP and PCT biomarkers for the collected blood. Blood samples will be shipped to the central laboratory overnight via Fed Ex. Marshfield Laboratory will document received date and time as well as time and date of analysis performed. Following assay of these biomarkers, all samples will be exhausted or destroyed, via biomedical waste procedures.

### ***Measuring red blood cell carbon isotope concentration***

Study samples will be stored in the freezer until batch shipped to the central laboratory, for carbon isotope analysis. Packed red cell samples will be shipped to the central laboratory overnight via a shipping service. The laboratory will document received date and time as well as time and date of analysis performed. Packed red cell samples will be combusted in an elemental analyzer and the carbon isotope ratio will be determined by isotope ratio mass spectrometry. All samples will be exhausted or destroyed, via biomedical waste procedures.

## 5.10 De-identification of samples

The master list will be destroyed two years after completion of study data analysis, and Isomark will notify the study site of this requirement at that time. After the master list is destroyed, samples will not be traceable to individual subjects.

## 5.11 Availability of test results

Data from laboratory tests will not be available in a timely manner, will not influence clinical care, and will not be revealed to the subject or subject's clinical care team.

## 5.12 Withdrawal of subjects

Table 1: Withdrawal of subjects				
Withdraw type	Specimens and data	Subject to be replaced?	Used for primary analysis?	Note
Infection Failure • Received antibiotic therapy during 7 days prior to hospital admission	All specimens and data will be kept.	Yes; will be labeled as a 'Screen Failure'	No	Screen failed subjects will be notified verbally of their withdrawal from the study.
Inclusion/Exclusion Failure • Have not met inclusion/exclusion criteria after original screening (e.g. later known cancer treatment or abx use prior to hospital admission)	All specimens and data will be kept.	Yes; will be labeled as a 'Screen Failure'	No	Screen failed subjects will be notified verbally of their withdrawal from the study.
By Investigator	All specimens and data obtained prior to withdrawing from study will be kept.	Yes	No	Subjects may be withdrawn from the study at any time at the discretion of the PI or the subject's attending physician with PI agreement. Withdrawn subjects will be notified verbally.
High frequency mechanical ventilation	Breath collection will be discontinued with high frequency ventilation. Development of infection will be monitored for 72 hours after the last breath sample is collected. All specimens and data will be retained in the study record.	No	No	High frequency ventilation is rarely used in adults because it has been shown to provide little or no benefit to subjects (17).

Table 1: Withdrawal of subjects				
Withdraw type	Specimens and data	Subject to be replaced?	Used for primary analysis?	Note
Surrogate who provided consent withdraws consent	All specimens and data obtained prior to subject withdrawing from study will be retained in the study record.	Yes, if withdrawn prior to Day 10	Yes, if withdrawn after Day 10	
Subject does not agree to participation when consent capacity regained	All data removed and samples destroyed unless already de-identified or used for safety analysis.	Yes	Yes, if samples and data de-identified or used for safety analysis	
Subject withdraws consent after initially providing consent	All specimens and data obtained prior to subject withdrawing from study will be retained in the study record.	Yes	Yes	
Unable to collect breath or blood samples through Day 5 (e.g., subject discharged or died, or continuous CPAP or BiPAP, or unable to obtain or provide breath sample after extubation)	All specimens and data will be retained in study record.	Yes	No	Medical records will be reviewed until discharge from the hospital or the IMC.
Sample collection outside of scheduled collections (e.g. extra samples-protocol deviation, samples outside of allowance window, etc)	All specimens and data will be retained in study record.	NO	Yes; subject will still be used in primary analysis, extra samples will NOT be used in primary analysis	Samples will be entered into EDC as extra samples, with note of their deviation.

## 6.0 Definitions

### 6.1 Study definitions

#### **Enrollment**

Subjects will be enrolled in the study as soon as possible after ICU admission, though not beyond 48 hours. A subject will be considered enrolled in the study if he/she meets all inclusion criteria, does not meet any exclusion criteria, and if he/she or a surrogate have provided informed consent and the first breath sample has been collected. A subject that later is withdrawn from the study will be included in the analysis following the criteria outlined in section 5.12.

#### **Systemic Inflammatory Response Syndrome (SIRS)**

SIRS is the presence of at least two of the following four criteria:

- T >38°C or <36°C
- Tachycardia, i.e. HR > 90 beats/min
- Tachypnea, i.e. RR > 20 breaths/min
- Increased leukocyte count >12,000 cells/mm^3 or decreased leukocyte count < 4,000 cells/mm^3 (not secondary to chemotherapy induced leukopenia), or >10% immature neutrophils

#### **Modified Early Warning System Criteria (MEWS):**

The modified early warning system is a tool to help monitor patients and improve how quickly a patient experiencing a sudden decline receives clinical care. The scoring is based on:

- Respiratory rate
- Heart rate
- Systolic blood pressure
- Conscious level
- Temperature
- Hourly urine output (for previous 2 hours)

#### **Antibiotic Use**

It is intended that subjects should not have an infection at the time of enrollment. Additionally, subjects should not be on a known course of antibiotics or antimicrobials within the seven days prior to hospital admission to be eligible for study participation.

Subsequent to enrollment, a subject who is discovered to have received systemic continuous antibiotic therapy within the seven days prior to hospital admission will be considered an infection failure, and will be withdrawn from the study. Perioperative antibiotics administered as routine standard of care are permitted.

#### **Source documents**

Source documents are the medical record(s) of a patient who has agreed to participate as a study subject. Examples of these original documents and data records include: hospital records, clinical and office charts, laboratory notes, memoranda, subjects' diaries or evaluation checklists, pharmacy dispensing records, recorded data from automated instruments, copies or transcriptions certified after verification of accuracy and completeness, microfiches, photographic negatives, microfilm or magnetic media, x-rays, subject files, and records kept at the pharmacy, at the laboratories, and at medico technical departments involved in the clinical trial.

#### **Source data**

Source data is all information, original records of clinical findings, observations, or other activities in a clinical trial necessary for the reconstruction and evaluation of the trial. Source data are contained in source documents.

## **Infection**

Any known or suspected infection, per the discretion of the investigator or attending physician(s) should be documented. If the subject has a known or suspected infection prior to consent/enrollment, the subject will not be eligible for study participation. If the subject has a known or suspected infection after enrollment, the principal findings leading to an infection diagnosis, clinical suspicion notes, shall be documented.

## **7.0 Data analysis and statistical considerations**

### **7.1 Sample size determination**

For trauma patients admitted to an ICU, the mean overall nosocomial infection rate is 6 to 18%. (9, 19, 20) The incidence rate of infection could be greater for all surgical ICU patients. Data collected to date indicate that a sustained decrease in BDV of 2.0‰ or more correlates with the onset of infection when the subject is used as his-her control. The average intra subject standard deviation (SD) across time points in 32 mechanically ventilated subjects previously studied was 1.16‰, regardless of the underlying medical conditions. The inter subject SD is expected to be 1.5‰ at most. Using the BDV measurements during the breath sample monitoring period (breath sample assessments every 4 hours), the expected overall SD of the mean BDV measurements (across time points) is less than 1.5‰.

Furthermore, during the monitoring period, the mean difference in the BDV between subjects who are diagnosed with a nosocomial infection and subjects not diagnosed with an infection is expected to be 2.0‰ or more (primary hypothesis). This difference will be considered to be the minimum difference with clinical importance.

Assuming that 5% of the subjects will have a confirmed nosocomial infection over the monitoring period and an overall standard deviation of 1.5‰, a total sample size of 100 subjects (5 infected and 95 non-infected) is required to detect a minimum clinically-important difference of 2.0‰ with at least 80% power at the two-sided 5% significance level.

If the actual rate of nosocomial infections is 10%, then the proposed total sample size of 100 subjects will provide 98% power to detect a mean difference of 2.0‰. Assuming SD to be 1.5‰ (at most) for the change in BDV before and after the diagnosis of an infection is made, a total sample size of 100 subjects and an infection rate of 5%, a mean decrease of 2.0‰ prior to and after the confirmed infection will be detected with 79% power at the one sided 5% significance level (secondary hypothesis).

If the rate of nosocomial infections is 10%, then the mean decrease of 2.0‰ will be detected with 99% power. The proposed sample size of 100 subjects is sufficient to provide accuracy in estimating the specificity of the BDV analyzer. That is, with a sample size of 100 and assuming that 95% of the subjects will have no confirmed nosocomial infection, the specificity will be estimated with a standard error of less than 5%, and the 95% confidence interval of the estimated specificity will be no greater than 20%.

To account for a missing value rate -- due to study withdrawal (see 5.12 Withdrawal of subjects) or infection failure of up to 10%, the total enrollment target is 110.

***The goal sample size of 100 subjects will be achieved through implementation of the protocol at more than one approved study site.***

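### Protocol 7.1 computes power for exactly 5 (or 10) infected subjects, but that count is random; at the planned 5% rate power averages 76% (two-sample) and 69% (paired), not at least 80% and 79%

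*Protocol*

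**What the plan says.** Protocol 7.1 starts from published rates in trauma ICU patients ("the mean overall nosocomial infection rate is 6 to 18"%) and adopts a lower planning rate: "Assuming that 5% of the subjects will have a confirmed nosocomial infection over the monitoring period". With "an overall standard deviation of 1.5"‰ and a two-sided 5% test, it concludes that "100 subjects (5 infected and 95 non-infected) is required to detect a minimum clinically-important difference of 2.0‰ with at least 80% power". It then gives three further powers:

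- Between-group comparison at a 10% rate: "If the actual rate of nosocomial infections is 10%, then the proposed total sample size of 100 subjects will provide 98% power".
- Before/after comparison at a 5% rate, SD of change 1.5‰: the 2.0‰ decrease "will be detected with 79% power at the one sided 5% significance level".
- Before/after comparison at a 10% rate: "then the mean decrease of 2.0‰ will be detected with 99% power".

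Protocol 7.2 names the tests: a two-sample t-test on the subject's averaged BDV, and a paired t-test for before versus after diagnosis. The size target is a number of subjects, 100, with 110 enrolled to cover losses of up to 10%. Protocol 3.0 enrols patients who are not suspected of infection at ICU admission. Neither 7.1 nor 7.4 continues enrolment until a given number of infections has occurred.

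**The concern.** The split into 5 and 95 is treated as a design constant, but it is an outcome. If each subject becomes infected independently with probability 5%, the number infected varies from trial to trial, and the smaller group determines almost all of the precision. Near 5, the power curve is steep and concave: moving from 5 infected to 4 costs more than moving from 5 to 6 gains. Power evaluated at the expected count therefore overstates the power averaged over the counts that can occur.

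The protocol attaches its claims to 100 subjects at a stated rate, not to 5 infections. A reader of 7.1 cannot see that a trial run exactly as planned would often have fewer than 5 infected subjects, or that the paired test might have almost no power. Protocol 3.0 says this study's estimates will be used to size the pivotal study, so its planners need to know how few infections it may yield.

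**Working it through.** **Inputs (Protocol 7.1 and 7.2).** Difference 2.0‰; SD 1.5‰ for both comparisons; N = 100; rates 5% and 10%; two-sample t-test at two-sided 5%; paired t-test at one-sided 5%.

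**Step 1. Reproduce the stated figures with a fixed infected count k.** Power comes from the noncentral t distribution.

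- Two-sample: noncentrality = 2.0 / (1.5 × √(1/k + 1/(100 − k))), 98 df, critical value 1.984. For k = 5 the noncentrality is 2.906.
- Paired: noncentrality = (2.0/1.5) × √k, k − 1 df. For k = 5 it is 2.981, with critical value 2.132 on 4 df.

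| Comparison | k | Stated | Reproduced |
|---|---|---|---|
| Two-sample | 5 | at least 80% | 82.1% |
| Two-sample | 10 | 98% | 97.7% |
| Paired, one-sided | 5 | 79% | 78.7% |
| Paired, one-sided | 10 | 99% | 98.7% |

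All four agree, so the method behind the stated figures is clear: k was set to its expected value.

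**Step 2. Power by infected count, with its probability under Binomial(100, 0.05).**

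| k | P(k) | Two-sample | Paired |
|---|---|---|---|
| 0 | 0.006 | not runnable | not runnable |
| 1 | 0.031 | 0.260 | not runnable |
| 2 | 0.081 | 0.456 | 0.233 |
| 3 | 0.140 | 0.615 | 0.458 |
| 4 | 0.178 | 0.735 | 0.652 |
| 5 | 0.180 | 0.821 | 0.787 |
| 6 | 0.150 | 0.880 | 0.874 |
| 7 | 0.106 | 0.921 | 0.927 |
| 8 or more | 0.128 | 0.948 or higher | 0.958 or higher |

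One infection fewer than 5 costs 9 points (two-sample) or 14 points (paired). One more gains 6 or 9. The chance of fewer than 5 infected is 43.6%. The chance of 2 or fewer is 11.8%, and there the paired test has at most 23% power. The chance of 0 or 1 is 3.7%, when the paired test cannot be run.

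**Step 3. Average.** Average power = Σ P(k) × power(k), with power set to 0 where the test cannot be run.

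| Rate | Two-sample | Paired, one-sided |
|---|---|---|
| 5% | 0.762 | 0.694 |
| 6% | 0.827 | 0.787 |
| 10% | 0.9549 | 0.9575 |
| 18% | 0.997 | 0.999 |

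A simulation of 100,000 trials at the 5% rate gives 0.761 and 0.695.

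**Step 4. Distance from the stated figures.** The average two-sample power reaches 80% at a true rate between 5.5% (79.7%) and 5.6% (80.3%). The paired power reaches 79% at about 6.0%. At a true rate of 5%, about 111 evaluable subjects give 80.2% for the two-sample test, and about 121 give 79.0% for the paired test.

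**The case against.** The strongest reply is that the protocol states its condition openly (5 infected, 95 not) and that, given it, the arithmetic is right. Computing power at the expected split is a common convention. Both planning values also look cautious. The 5% rate is below the cited 6 to 18%, and 1.5‰ is described as an upper limit for the SD. At a 6% rate the averages are 83% and 79%, so both claims are essentially met. At 5% with an SD of 1.4‰ the two-sample average is 80.6%, though the paired one is still 73%. This is also a pilot study, and no analysis or decision rule changes.

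Much of this stands. It shows that the study is not necessarily underpowered, and that the fault is a missing allowance for a random count, not a slip in calculation. It does not rescue the claims as stated. They are made for 100 subjects at a 5% rate and an SD of 1.5‰, and at those values the averages are 76% and 69%.

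Three narrower points do not change this:

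- Leaving out trials where the test cannot be run raises the averages only to 77% (two-sample) and 72% (paired).
- The extra 10 enrolled subjects are reserved for losses. If all 110 were evaluable, the averages would be 79.9% and 74.3%.
- The SAP's sizing on 97 infection and 97 non-infection events belongs to different hypotheses and a 50% infection rate, so it does not correct Protocol 7.1.

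**Conclusion.** The concern holds. At the protocol's own 5% rate and 1.5‰ SD, 100 subjects give 76% average power for the two-sample comparison (82% at exactly 5 infected; at least 80% stated) and 69% for the paired comparison (79% stated). At 10% the figures are 95% and 96% against 98% and 99%, which leaves adequacy untouched. The result assumes independent infections at a common rate, and counts a trial in which the test cannot be run as a failure. It is sensitive to the rate: a true rate of about 5.6% for the two-sample test, or 6.0% for the paired test, restores the stated powers.

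**What to change.** Restate the power paragraphs of Protocol 7.1, for example:

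*Allowing for the random number of infections, with a difference of 2.0‰ and an SD of 1.5‰, 100 evaluable subjects give average power of 76% (two-sample, two-sided 5%) and 69% (paired, one-sided 5%) at a 5% infection rate, 83% and 79% at 6%, and 95% and 96% at 10%. Trials with too few infected subjects to run the test are counted as failures. At a 5% rate the probability of fewer than 5 infected subjects is 44%.*

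The sample size need not change. The cost is a protocol wording change and less favourable stated figures at the 5% rate.
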